Section 7.7 End of Treatment Visit (EOT)	All subjects will complete an EOT visit. For subjects who complete the 36-month treatment period and who have been off romiplostim and other medications for ITP (concomitant or rescue) for 4 weeks or more, the EOT visit will be the final study visit and will occur after the completion of the 36-month treatment period. For subjects ending the 36-month treatment period for non-response or other reasons while still receiving romiplostim, this visit will be 1 week after the last administration of romiplostim.	All subjects will complete an EOT visit. For subjects who complete the 36-month treatment period and who have been off romiplostim and other medications for ITP (concomitant or rescue) for 4 weeks or more, the EOT visit will be the final study visit and will occur after the completion of the 36-month treatment period. For subjects ending the 36-month treatment period for non-response or other reasons while still receiving romiplostim, this visit will be 1 week after the last administration of romiplostim. In addition, a bone marrow biopsy and aspirate should be obtained for discontinued subjects who have not yet had a cohort-defined bone marrow biopsy performed.

Table 1. Summary of Changes

Protocol Section	Text in Protocol	Text For the EU, Switzerland, and Turkey
Section 7.8 End of Study Visit	
Four weeks after the last dose of romiplostim for subjects who end the 36-month treatment period for non-response or other reasons while still receiving romiplostim will have an EOS visit.
 
The following assessments will be completed at the EOS visit:
 
 • local lab platelet count • serious adverse event reporting • documentation of concomitant and rescue medications 	
Four weeks after the last dose of romiplostim for subjects who end the 36-month treatment period for non-response or other reasons while still receiving romiplostim will have an EOS visit.
 
The following assessments will be completed at the EOS visit:
 
 • local lab platelet count • serious adverse event reporting • documentation of concomitant and rescue medications • Bone marrow biopsy and aspirate (only for subjects with collagen or a change to grade 3 or 4 reticulín)

Table 1. Summary of Changes

Protocol Section	Text in Protocol	Text For the EU, Switzerland, and Turkey
Section 10.1.1 Study Endpoints Primary Endpoint	
 The percentage of time with a platelet count of $\geq 50 \times 10^9/L$ starting from week 2 in the first 6 months of the treatment period without rescue medication use within the past 4 weeks 	
 The percentage of time with a platelet count of $\geq 50 \times 10^9/L$ starting from week 2 in the first 6 months of the treatment period without rescue medication use within the past 4 weeks Evaluation of bone marrow changes after Year 1 or Year 2 for the following: 
 Incidence of collagen as evidenced by trichrome staining (using the modified Bauermeister grading scale) after romiplostim exposure Incidence of bone marrow reticulin increases in severity ≥ 2 grades (ie, grade 0 to 2-4, 1 to 3-4, 2 to 4), compared to baseline, or an increase to grade 3 or grade 4 as evidenced by reticulin silver staining using the modified Bauermeister grading scale after romiplostim exposure Incidence of bone marrow abnormalities (eg, myelodysplastic syndrome, monosomy 7) as evidenced by cytogenetics and fluorescence in situ hybridization

Table 1. Summary of Changes

Protocol Section	Text in Protocol	Text For the EU, Switzerland, and Turkey
Section 10.1.1 Study Endpoints Secondary Endpoint	
 The percentage of time with a platelet count of $\geq 50 \times 10^9/L$ starting from week 2 until the end of the treatment period without rescue medication use within the past 4 weeks The percentage of time with an increase in platelet count $\geq 20 \times 10^9/L$ above baseline starting from week 2 until the end of the treatment period without rescue medication use in the past 4 weeks Subject incidence of rescue ITP medications used The incidence of anti-romiplostim neutralizing antibodies and cross reactive antibodies to TPO at any time during the study The incidence of adverse events, including clinically significant changes in laboratory values 	
 The percentage of time with a platelet count of $\geq 50 \times 10^9/L$ starting from week 2 until the end of the treatment period without rescue medication use within the past 4 weeks The percentage of time with an increase in platelet count $\geq 20 \times 10^9/L$ above baseline starting from week 2 until the end of the treatment period without rescue medication use in the past 4 weeks. Subject incidence of rescue ITP medications used The incidence of anti-romiplostim neutralizing antibodies and cross reactive antibodies to TPO at any time during the study The incidence of adverse events, including clinically significant changes in laboratory values The incidence of increased reticulin as evidenced by silver staining at Year 1 or Year 2, after exposure to romiplostim

Table 1. Summary of Changes

Protocol Section	Text in Protocol	Text For the EU, Switzerland, and Turkey
Section 10.2 Sample Size Considerations	Not applicable	
A sample size of at least 60 subjects was selected for subjects undergoing bone marrow evaluations. The sample size was chosen to provide an assessment/estimation of the development of bone marrow abnormalities (eg, collagen as evidenced by trichrome staining) at Year 1 or Year 2 after romiplostim exposure using the modified Bauermeister grading scale.
 
With 30 subjects in each cohort, the number of evaluable bone marrow results in each cohort is expected to be between 20 and 25. The assumption of 20 to 25 evaluable subjects is based on the approximate 30% rate of repeat inevaluable or missing bone marrow samples observed in the current Amgen adult ITP bone marrow study with romiplostim (Study 20080009). The 95% exact confidence intervals for outcomes of bone marrow abnormalities when there are 20 and 25 evaluable bone marrow results are described in Table 4.
 
No historical data are available regarding the change in bone marrow morphology in this patient population. Clinical data from adult ITP subjects receiving romiplostim demonstrated that increases in bone marrow reticulin (or the presence of reticulin on study) were observed in 3.7% (10 of 271 of subjects: romiplostim 120-day safety update dataset used). However the potential incidence rate could be higher or lower given that bone marrow assessments were not systematically performed on all subjects during clinical studies.

Table 1. Summary of Changes

Protocol Section	Text in Protocol	Text For the EU, Switzerland, and Turkey																																																																
Section 10.2 Sample Size Considerations (continued)		
Table 4. 95% Exact Confidence Intervals for the Incidence Rate of a Bone Marrow Abnormality
 
  
 Number of Subjects with Evaluable Bone Marrow = 20	
 
 Number of Subjects With a Bone Marrow Abnormality	Incidence Rate	95% CI Lower Bound	95% CI Upper Bound	
   
 0	0.0%	0.0%	16.8%	
 
 1	5.0%	0.1%	24.9%	
 
 2	10.0%	1.2%	31.7%	
 
 3	15.0%	3.2%	37.9%	
 
 4	20.0%	5.7%	43.7%	
 
 5	25.0%	8.7%	49.1%	
  
 
  
 Number of Subjects with Evaluable Bone Marrow = 25	
 
 Number of Subjects With a Bone Marrow Abnormality	Incidence Rate	95% CI Lower Bound	95% CI Upper Bound	
   
 0	0.0%	0.0%	13.7%	
 
 1	4.0%	0.1%	20.4%	
 
 2	8.0%	1.0%	26.0%	
 
 3	12.0%	2.5%	31.2%	
 
 4	16.0%	4.5%	36.1%	
 
 5	20.0%	6.8%	40.7%	
  
	Number of Subjects with Evaluable Bone Marrow = 20				Number of Subjects With a Bone Marrow Abnormality	Incidence Rate	95% CI Lower Bound	95% CI Upper Bound	0	0.0%	0.0%	16.8%	1	5.0%	0.1%	24.9%	2	10.0%	1.2%	31.7%	3	15.0%	3.2%	37.9%	4	20.0%	5.7%	43.7%	5	25.0%	8.7%	49.1%	Number of Subjects with Evaluable Bone Marrow = 25				Number of Subjects With a Bone Marrow Abnormality	Incidence Rate	95% CI Lower Bound	95% CI Upper Bound	0	0.0%	0.0%	13.7%	1	4.0%	0.1%	20.4%	2	8.0%	1.0%	26.0%	3	12.0%	2.5%	31.2%	4	16.0%	4.5%	36.1%	5	20.0%	6.8%	40.7%
Number of Subjects with Evaluable Bone Marrow = 20																																																																		
Number of Subjects With a Bone Marrow Abnormality	Incidence Rate	95% CI Lower Bound	95% CI Upper Bound																																																															
0	0.0%	0.0%	16.8%																																																															
1	5.0%	0.1%	24.9%																																																															
2	10.0%	1.2%	31.7%																																																															
3	15.0%	3.2%	37.9%																																																															
4	20.0%	5.7%	43.7%																																																															
5	25.0%	8.7%	49.1%																																																															
Number of Subjects with Evaluable Bone Marrow = 25																																																																		
Number of Subjects With a Bone Marrow Abnormality	Incidence Rate	95% CI Lower Bound	95% CI Upper Bound																																																															
0	0.0%	0.0%	13.7%																																																															
1	4.0%	0.1%	20.4%																																																															
2	8.0%	1.0%	26.0%																																																															
3	12.0%	2.5%	31.2%																																																															
4	16.0%	4.5%	36.1%																																																															
5	20.0%	6.8%	40.7%																																																															

Page 21 of 23

Table 1. Summary of Changes

Protocol Section	Text in Protocol	Text For the EU, Switzerland, and Turkey
Section 10.3.1 Interim Analyses	Interim analyses will be conducted to support regulatory filings, and accumulated data for this study will be summarized to provide ongoing assessments of the safety of romiplostim. These interim analyses will occur at least annually until the end of the study.	
Interim analyses will be conducted to support regulatory filings, and accumulated data for this study will be summarized to provide ongoing assessments of the safety of romiplostim. These interim analyses will occur at least annually until the end of the study.
 
A Bone Marrow Panel comprised of experts in the treatment of ITP and interpreting bone marrow pathology will convene approximately one time per cohort when all bone marrow biopsy samples have been evaluated for each respective cohort. The Bone Marrow Panel will independently review the central lab bone marrow results and report those results to Amgen once each respective cohort has completed. The bone marrow panel is not chartered to make recommendations to study conduct.
 
A report will be generated including details of study compliance, the number of samples submitted and bone marrow biopsy results. Additional data may be summarized at intervals throughout the duration of the study. These data may be provided for regulatory or publication activities.

Table 1. Summary of Changes

Protocol Section	Text in Protocol	Text For the EU, Switzerland, and Turkey
Section 10.3.4 Additional Analysis, Add section 10.3.4.4 Bone Marrow Analysis	Not applicable	Section 10.3.4.4 Bone Marrow Analysis The number and percentage of subjects who develop collagen as evidenced by trichrome staining at Year 1 or Year 2, will be summarized by study cohort, splenectomy status at baseline, years since diagnosis (≤ 3 vs > 3 years), age at enrollment (≥ 1 year to < 6 years; 6 years to < 12 years; 12 years to < 18 years) and maximum doses and drug exposures if appropriate. In addition, logistic regression may be used to investigate the association of bone marrow abnormality and potential predictive factors. The number and percentage of subjects with collagen as evidenced by trichrome staining 12 weeks after romiplostim discontinuation among subjects who developed collagen will be summarized. The number and percentage of subjects with bone marrow reticulin increases by ≥ 2 severity grades or any increase to grade 4 (ie, grade 0 to 2-4, 1 to 3-4, 2 to 4), or change to grade 3 to 4 over baseline as evidenced by reticulin silver staining at Year 1 or Year 2, post romiplostim exposure using the modified Bauermeister grading scale will be summarized. The number and percentage of subjects with improvement of reticulin to a grade of ≤ 2 for subjects who developed grade 3 reticulin after initial exposure to romiplostim as measured by the modified Bauermeister grading scale will be summarized.

Product: Romiplostim
Protocol Number: 20101221 (Supplement Version 2)
Date: 15 July 2014

Page 1 of 2

Supplement Version #2

Protocol Supplement for the European Union (EU), Switzerland, and Turkey

**Protocol Title: A Single Arm, Open-label, Long-term Efficacy and Safety Study of
Romiplostim in Thrombocytopenic Pediatric Subjects With Immune
Thrombocytopenia (ITP)**

Amgen Protocol Number 20101221

EudraCT number 2011-005019-96

Amendment Date: 15 July 2014

Rationale:

As a result of regulatory reviews, modifications have been made to the numbering and content of the supplement inclusion criteria

Product: Romiplostim
Protocol Number: 20101221 (Supplement Version 2)
Date: 15 July 2014

Page 2 of 2

Description of Changes:

[Section: Header of the Document](#)

Replace: 15 April 2014

With: **15 July 2014**

[Section: Title Page,](#)

Add: **Supplement Version #2: 15 July 2014**

[Page 13, Section 4.1: Inclusion Criteria](#)

Renumber inclusion criteria 4.1.6 with 4.1.7

[Page 13, Section 4.1: Inclusion Criteria](#)

Renumber inclusion criteria 4.1.7 with 4.1.8

Replace:

Baseline bone marrow reticulin grade of 0, 1, 2, or 3 according to the modified Bauermeister grading scale, as assessed by central laboratory

With:

A reticulin grade of 0, 1, 2, or 3 according to the modified Bauermeister grading scale, as assessed by central laboratory from a bone marrow biopsy performed within 1 year prior to planned first dose of romiplostim or consent to a pre-treatment bone marrow biopsy and aspirate prior to planned first dose of romiplostim

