Section 1.1 Primary Objectives	The primary objective is to describe the percentage of time that pediatric subjects with immune thrombocytopenia (ITP) have a platelet response in the first 6 months from the start of treatment with romiplostim.	The primary objective(s) are as follows: 
• to describe the percentage of time that pediatric subjects with immune thrombocytopenia (ITP) have a platelet response in the first 6 months from the start of treatment with romiplostim• to evaluate incidence of changes in bone marrow findings at Year 1 and Year 2 after initial exposure to romiplostim

Page 8 of 23

Table 1. Summary of Changes

Protocol Section	Text in Protocol	Text For the EU, Switzerland, and Turkey
Section 1.2 Secondary Objectives	
The secondary objectives of the study are:
 
 To describe the percentage of time that pediatric subjects with ITP have a platelet response over the study duration To describe the percentage of time that pediatric subjects with ITP have an increase in platelet count $\geq 20 \times 10^9/L$ above baseline over the study duration To describe the use of rescue ITP medications To describe the incidence of antibody formation To describe the safety of romiplostim as a long-term treatment in pediatric thrombocytopenic subjects with ITP 	
The secondary objectives of the study are:
 
 The percentage of time with a platelet count of $\geq 50 \times 10^9/L$ starting from week 2 until the end of the treatment period without rescue medication use within the past 4 weeks The percentage of time with an increase in platelet count $\geq 20 \times 10^9/L$ above baseline starting from week 2 until the end of the treatment period without rescue medication use in the past 4 weeks. Subject incidence of rescue ITP medications used The incidence of anti-romiplostim neutralizing antibodies and cross-reactive antibodies to TPO at any time during the study The incidence of adverse events, including clinically significant changes in laboratory values The incidence of increased reticulin as evidenced by silver staining at Year 1 or Year 2, after exposure to romiplostim

Table 1. Summary of Changes

Protocol Section	Text in Protocol	Text For the EU, Switzerland, and Turkey

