a **Bone Marrow Biopsy:** A baseline bone marrow biopsy and aspirate is required to determine eligibility; this can be either a bone marrow biopsy within 1 year prior to planned first dose of romiplostim (with available bone marrow tissue block or a minimum of 5 unstained, evaluable histological slides to send to a central laboratory) or a pre-treatment bone marrow biopsy and aspirate within 3 weeks prior to planned first dose of romiplostim. Central laboratory evaluation is required prior to the first dose of romiplostim. A further bone marrow biopsy and aspirate is required at Year 1 or Year 2, depending on the cohort in which the subject is enrolled (as designated by IVRS). Additional bone marrow biopsies and aspirates may be performed if clinically indicated at the discretion of the investigator and/or Amgen.

b **End of Treatment (EOT):** Subjects who are non-responders and withdraw from the study will require a bone marrow biopsy and aspirate at the EOT visit. A bone marrow biopsy and aspirate should be obtained for discontinued subjects who have not yet had a cohort-defined bone marrow biopsy performed.

c **End of Study (EOS):** EOS will be delayed for subjects who are withdrawn from the study due to the presence of collagen, or subjects who have a change to grade 3 reticulin, per central laboratory evaluation of a bone marrow biopsy. These subjects will complete an EOS visit 12 weeks after discontinuation of romiplostim and will require a repeat bone marrow biopsy.

Table 1. Summary of Changes

Protocol Section	Text in Protocol	Text For the EU, Switzerland, and Turkey

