Add new section 7.1.4 Bone Marrow Biopsy	Not applicable	
Bone Marrow Biopsy
 
For the protocol supplement, a baseline bone marrow biopsy and aspirate is required to determine eligibility; central laboratory evaluation is required prior to first dose of romiplostim. A baseline bone marrow biopsy can be either a bone marrow biopsy within 1 year prior to the planned first dose of romiplostim (with available bone marrow tissue block or a minimum of 5 unstained, evaluable histological slides to send to a central laboratory) or a pre-treatment bone marrow biopsy and aspirate within 3 weeks prior to planned first dose of romiplostim.
 
A repeat bone marrow biopsy and aspirate is required at Year 1 or Year 2 (\pm 4 week window) depending on the cohort assignment. A bone marrow biopsy and aspirate should be obtained for discontinued subjects who have not yet had a cohort-defined bone marrow biopsy performed.
 
Should collagen be detected in any subjects during the course of the study, study drug will be discontinued and the subject will undergo an EOT visit. A repeat bone marrow biopsy will be required 12 weeks later at the EOS visit (+ 2 week window) for subjects who are withdrawn from the study due to the presence of collagen.
 
Subjects who have a change to grade 3 reticulin, per central laboratory evaluation of a bone marrow biopsy, will undergo a repeat bone marrow biopsy 12 weeks after their last dose of romiplostim at the EOS visit (+ 2 week window).
 
Subjects who are considered non-responders and will be discontinued from the study will require a bone marrow biopsy and aspirate sample to be taken at the EOT visit (+ 2 week window). A repeat bone marrow biopsy will also be required 12 weeks later at EOS visit (+ 2 week window) for non-responders who have a change to grade 3 reticulin or collagen, per central laboratory evaluation of a bone marrow biopsy.
 
Bone marrow biopsies and aspirates where applicable, will be sent to a central laboratory for reticulin and collagen staining and analysis. Refer to Central Laboratory Manual for instructions on collection, preparation, storage, and shipment of samples. The modified Bauermeister Scale (Bauermeister, 1971) will be used for this study. Subjects with a reticulin grade of 0, 1, 2, or 3 will be eligible for this study.

Table 1. Summary of Changes

Protocol Section	Text in Protocol	Text For the EU, Switzerland, and Turkey

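### Does the EU supplement define its primary marrow incidence in two conflicting ways, at the scheduled biopsy and at any biopsy after exposure?

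*Protocol*

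**What the plan says.** The supplement for the EU, Switzerland and Turkey adds marrow change as a primary endpoint in at least 60 children. They form two cohorts of at least 30, with a repeat biopsy at Year 1 in one and at Year 2 in the other (Sections 3.1 and 3.3).

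Timing of the measure:
- Section 1.1, objective: "to evaluate incidence of changes in bone marrow findings at Year 1 and Year 2 after initial exposure to romiplostim".
- Section 10.1.1, endpoint: a lead-in places the evaluation after Year 1 or Year 2 (the synopsis joins the two years with *and*). Three measures follow. The collagen one reads "Incidence of collagen as evidenced by trichrome staining (using the modified Bauermeister grading scale) after romiplostim exposure". The cytogenetic one has no time phrase of its own.
- Section 10.2, sample size: the estimate is made "at Year 1 or Year 2 after romiplostim exposure using the modified Bauermeister grading scale".
- Section 10.3.4.4, analysis: the incidence covers those "who develop collagen as evidenced by trichrome staining at Year 1 or Year 2, will be summarized by study cohort". A follow-up table gives collagen status "12 weeks after romiplostim discontinuation among subjects who developed collagen will be summarized".

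Biopsies away from the schedule:
- Table 2b, footnote b: "Subjects who are non-responders and withdraw from the study will require a bone marrow biopsy and aspirate at the EOT visit". The same footnote and Sections 7.1.4 and 7.7 also ask for one in discontinued children who lack their cohort biopsy.
- Section 7.1.4 allows clinically indicated biopsies, with available material read centrally.
- Section 7.1.4 on collagen: "Should collagen be detected in any subjects during the course of the study, study drug will be discontinued". Table 2b, footnote c, adds: "These subjects will complete an EOS visit 12 weeks after discontinuation of romiplostim and will require a repeat bone marrow biopsy".

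The SAP is written to the protocol of 15 January 2014, before the supplement's first version of 15 April 2014, and contains no marrow analysis.

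**The concern.** Set beside each other without their context, the collagen bullet in Section 10.1.1 looks open-ended and the incidence sentence in Section 10.3.4.4 looks tied to a scheduled biopsy. The supplement's own rules produce two kinds of child for whom these readings differ.

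1. **Early finding.** Collagen on an off-schedule biopsy ends treatment. The child may leave before the cohort window opens and so never have a Year 1 or Year 2 biopsy. The 12-week follow-up table would include this child, while the incidence table, read literally, would not.
2. **Late finding.** A Year 1 cohort child with a clean Year 1 biopsy stays on drug and can have a non-responder biopsy at end of treatment in year 2 or 3. A new abnormality there follows exposure but is not at Year 1.

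At stake is which percentage and exact interval are reported for a primary endpoint that serves binding elements of the paediatric investigation plan. With 20 to 25 evaluable children per cohort, one case is worth 4 to 5 percentage points.

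**Working it through.** **1. The plan's own figures.** Section 10.2 expects 20 to 25 evaluable results from 30 children, citing about 30% loss: 30 × (1 − 0.30) = 21, inside that range. Table 4 gives exact intervals. For zero events the upper limit is 1 − 0.025^(1/n):
- n = 20: 1 − 0.025^(1/20) = 16.8%
- n = 25: 1 − 0.025^(1/25) = 13.7%

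All 12 intervals of Table 4 reproduce by the Clopper-Pearson method.

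**2. When the readings could part.** Take Year 1 as week 52 and Year 2 as week 104, with the ±4 weeks of Section 7.1.4.
- The windows are weeks 48 to 56 and 100 to 108.
- The final visit of a child with collagen is 12 weeks after discontinuation. The child is gone before the window opens if the last dose is before week 48 − 12 = 36 (Year 1 cohort) or 100 − 12 = 88 (Year 2 cohort).
- Treatment time left after the window, out of 156 weeks, is 156 − 56 = 100 and 156 − 108 = 48.

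These are spans of calendar time, not chances of a positive off-schedule biopsy.

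**3. Size if one case occurs (assumed; no count is given in the documents).**

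| Situation | Scheduled biopsies only | All post-baseline biopsies |
|---|---|---|
| Early, 20 scheduled | 0/20: 0% (0 to 16.8) | 1/21: 4.8% (0.1 to 23.8) |
| Early, 25 scheduled | 0/25: 0% (0 to 13.7) | 1/26: 3.8% (0.1 to 19.6) |
| Late, 20 scheduled | 0/20: 0% (0 to 16.8) | 1/20: 5.0% (0.1 to 24.9) |

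For scale, the adult rate in Section 10.2 is 10/271 = 3.7%, which gives 20 × 10/271 = 0.74 to 25 × 10/271 = 0.92 cases per cohort. That rate is for reticulin, includes anything found on schedule, and is said to be possibly too high or too low. For collagen, protocol Section 2.5 reports none so far in the adult one-year and two-year cohorts.

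**4. The texts side by side.**
- The lead-in in Section 10.1.1 governs its list. The cytogenetic bullet can take its timing from nowhere else.
- The two phrases are partners, not rivals. The objective, the sample-size text and the reticulin sentence of Section 10.3.4.4 each place the Year label and the reference to exposure in one clause. After exposure can simply mean post-baseline.
- Section 3.3 identifies the cohorts by the same Year labels, and Section 10.3.4.4 tabulates by cohort. A biopsy requested because the cohort biopsy is missing is most naturally read as standing in for it.
- In Section 10.3.4.4 the follow-up sentence comes straight after the incidence paragraph, so its children can be read as those just counted. On that reading the two tables agree.
- The variations that do exist are *at* against *after*, and *and* against *or*. Neither makes the endpoint open-ended.

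**The case for a change.** The best case for a change is that the gap is real and Section 10.3.4.4 is the only detailed rule, since the SAP is silent on marrow. Off-schedule biopsies are foreseeable. Under the protocol's titration a child can first receive the maximum dose in week 10, and four further weeks bring the non-responder criterion to about week 14, some 34 weeks before the Year 1 window opens at week 48. For non-responders the end-of-treatment biopsy is worded as a requirement, and footnote b and Section 7.1.4 do not make it depend on a missing cohort biopsy (Section 7.7 carries only the conditional request). With so few children, the counting convention could decide whether the reported incidence is zero.

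Much of this stands. No sentence assigns off-schedule biopsies to a numerator or denominator, the time phrase wavers, and the follow-up table states no time limit. What does not stand is the step from there to a contradiction. Only the non-responder biopsy is mandatory; the others are worded as *should* or *may*. The 12-week biopsy repeats a finding already made and adds no case. Nothing in the text excludes an off-schedule result: Section 10.3.1 has an expert panel review the central results for each cohort and provides for a report of the samples submitted and the biopsy results.

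**Conclusion.** No change is needed. The supplement does not hold two rival definitions; it leaves out a tabulation detail that analysts fill sensibly. An evaluable, centrally read biopsy taken in place of a missed cohort biopsy counts in that cohort. A finding first made after the window is listed with its time on romiplostim, because adding it to a Year 1 percentage would mix exposure times.

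A rewrite would gain little. Counting every biopsy up to the end of the window, for example, would introduce a third definition and still leave the late case at 0/20.

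The possible effect is one case in 20 to 26 children, about 4 to 5 percentage points, in a descriptive estimate whose interval already reaches 13.7% to 16.8% with no events. This rests on two assumptions: that the inclusive reading is used for substitute biopsies, which is the natural one, and that off-schedule positives are few, which the documents neither state nor contradict.
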